6.3.2 Storage

Study product will be securely stored at controlled room temperature with excursions permitted from 15°C-30°C until required for administration. Tenofovir gel should be stored away from direct sunlight.

6.3.3 Dispensing

Tenofovir gel will be dispensed either directly (control arm) or indirectly (intervention arm) by designated individuals to enrolled study participants as per Standard Operating Procedures (SOPs) in quantities expected to be sufficient until the participant's next follow-up visit.

In the event that a participant needs additional supplies between visits, she will be instructed to contact the study clinic to request additional supplies. Study participants will be asked to return all previously dispensed applicators at each visit. All returned used and unused applicators will be reconciled with the number dispensed to the participant and the outcome logged, All returned applicators will be stored until checked by the study monitors and thereafter disposed of in accordance with Good Pharmacy Practice. Unused applicators that were never dispensed will be stored at the study pharmacy until destroyed. Further details of the dispensing procedures are outlined in the Study Specific Pharmacy Procedures Manual.

6.4 Adherence counseling

Adherence counseling will be provided to study participants upon enrollment and additionally at each study visit. Adherence counselors / nurses will be provided with a set of job aids, including a reference guide to assist with and standardize adherence support counseling. Techniques based on motivational interviewing will be used to address such topics as participant-centered strategies to remember to use the products before and after sex, to ensure the availability of the products both in the home and away from home, and to identify and discuss various challenges and situations that may impede product use. Counseling will include reminders to contact study staff with questions about gel use and requests for additional supplies. For participants experiencing adherence challenges, every effort will be made to identify customized strategies to increase their rates of product use throughout the course of the study.

6.5 Adherence assessment

Data on adherence to the gel use regimen will be collected at each study visit via brief interviewer-administered instruments. Additionally, genital specimens collected during the trial at study months 6, 12, 18, 24, study exit and from suspected HIV seroconvertors will be archived for analysis of markers of product adherence to enhance interpretation of the results of the trial.

6.6 Discontinuation of product

Study participants will be discontinued from using tenofovir gel by the Principal Investigators and their designees in the event that they experience a Serious Adverse Event (SAE) that is judged by the study clinician or designee to be related to gel use (see Section 8.2). Participants who become pregnant will discontinue gel use and will only resume gel use when their pregnancy test reverts to negative. The Principal Investigators and designees also may at their discretion discontinue gel use — temporarily or permanently — among participants who:

- Experience an AE judged to be related to gel use.
- Have a pelvic examination finding involving deep epithelial disruption that is not resolving.
- Are unable or unwilling to comply with required study procedures.
- Otherwise might be put at undue risk to their safety and well-being by continuing gel use.

Gel use will be permanently discontinued when HIV infection has been confirmed according to the algorithm in Appendix I.

For participants who temporarily discontinue gel use, every effort will be made to complete all protocol-specified follow-up visits and procedures (except study product dispensing procedures). Designated staff will document all changes in gel regimen, and the reason for the change, on applicable Case Report Forms (CRFs).

6.7 Concomitant medications

Enrolled study participants may continue use of all concomitant medications, including prescription, non-prescription, traditional, and other preparations during this study. As noted in Section 6.2, participants will be encouraged to avoid douching and the use of vaginally-applied medications/preparations. All concomitant medications used by participants throughout the course of the study will be reported on applicable CRFs.

7. STUDY PROCEDURES

The schedule of evaluations for the two study arms are provided in Appendix IV. Study specific training will be provided to all study staff to ensure that study procedures are undertaken in a standardized manner. The protocol, SOPs and Study Specific Procedures (SSP) manual will guide this process. Following study initiation, study specific training will be undertaken annually and/or if there are any protocol and/or procedural changes.

7.1 Screening visit (up to day -30)

If all the required screening procedures cannot be completed in a single visit, then multiple visits may be conducted as necessary. For potential participants who do not meet the study eligibility criteria, the screening process will be discontinued when ineligibility is determined.

Screening will be completed in a stepwise manner. The first step includes the provision of introductory study information and obtaining informed consent for screening procedures. HIV testing in the context of pre- and post-test counseling will be done and only HIV negative participants will continue with the screening process.

The following procedures will be completed:

7.1.1 *Administrative, behavioral, and regulatory procedures*

- Informed consent for screening
- Assignment of a screening number
- Collection of the following:
 - Demographic information

- Locator information
- Eligibility assessment
- HIV/STI risk reduction counseling and provision of condoms

7.1.2 Clinical procedures

- Focused medical and menstrual history and ascertainment of concomitant medications
- Physical examination
- Assessing for STIs and other genitourinary symptoms requiring treatment
- Pelvic examination (only if indicated)
- Blood draw

7.1.3 Laboratory procedures

- Urine pregnancy testing
- HIV rapid testing
- Creatinine level (serum)

7.2 Enrollment visit (day 0)

Women found to be eligible after screening, will be scheduled for an enrollment visit. Informed consent for study participation will be administered once eligibility for enrolment has been confirmed; thereafter enrollment (or “on-study”) procedures will be conducted.

7.2.1 Administrative, behavioral, and regulatory procedures

- Confirm eligibility
- Informed consent for enrollment and stored specimens
- Update locator information
- HIV/STI risk reduction counseling and provision of condoms
- Randomization and participant identification (PID) number allocation
- Baseline data collection including sexual behavior
- Family planning counseling
- Product adherence counseling

7.2.2 Clinical procedures

- Review/update pre-existing conditions
- Inventory and documentation of concomitant medications
- Physical examination
- Pelvic examination
- Genital specimen collection
- Blood draw
- Demonstration of product use and onsite gel insertion

7.2.3 Pharmacy-related procedures

- Provision of tenofovir gel and instructions
- Update accountability log

7.2.4 Laboratory procedures

- Urine pregnancy testing if no negative pregnancy test result in last 21 days prior to enrollment
- Serum and plasma archive
- HBV assay
- HSV-2 assay
- Hematology – full blood count
- Chemistry – creatinine, urea and electrolytes, calcium and phosphate
- Liver function tests
- Genital specimen archive

7.3 Follow-up visits

Women randomized to the intervention arm will attend monthly visits for the first 3 months of study participation. Thereafter, gel provision and monitoring will be scheduled to coincide with each participant’s

routinely scheduled family planning visits (typically every 2-3 months). Follow-up visits for women enrolled into the control arm are scheduled throughout the study follow-up period on a 28-day schedule. The visit window around a study visit is 14 days on either side. In addition to the regular follow-up requirements, additional procedures are done at study months 6, 12, 18, 24 and study exit for all participants. For participants who do not complete scheduled visits within the allowable window, the visit will be considered “missed” and relevant CRFs will be completed to document the missed visit. However, for participants who miss their month 6, 12, 18 or 24 visits, the study procedures specified to take place at these visits will be conducted at the participants’ next visit.

Participants who become pregnant during the study will be followed as usual, but gel will be withheld until they have a negative pregnancy test. For participants who become HIV infected during the study, product will be permanently discontinued once diagnosis of a HIV positive status is confirmed. HIV seroconvertors in the trial will be referred to the CAPRISA 002 Acute Infection study and/or the CAPRISA 009 treatment study for further care and follow-up. For women opting not to enroll in the CAPRISA 002 or CAPRISA 009 study they will be referred to the CAT Programme at the urban or rural site as appropriate or to other sources of care and support available to these communities.

Follow-up study visits occur monthly for the first 3 months and 2-3 monthly thereafter up to and including the study exit visit for participants in the intervention arm and monthly up to and including the study exit visit for participants in the control arm. The following study procedures will be performed during study follow-up:

7.3.1 Administrative, behavioral, and regulatory procedures

- Locator information update:
 - Each study visit
- HIV/STI risk reduction counseling:
 - Each study visit
 - Additionally when clinically indicated
- Distribution of condoms:
 - Each study visit
- Inventory and documentation of concomitant medications:
 - when indicated and at study exit
- Sexual behavioral and study product reconciliation:
 - Each study visit
- Family planning counseling:
 - Each study visit
- Service acceptability assessment:
 - At months 6, 12, 18, 24 and study exit
- Product acceptability assessment:
 - At months 6, 12, 18, 24 and study exit

7.3.2 Clinical procedures

- Interval (i.e. since last visit) medical and menstrual history including detailed intermenstrual bleeding history and AE assessment and concomitant medication review
 - Each study visit
 - Additionally when indicated
- Pelvic examination
 - At months 6, 12, 18, 24 and study exit
 - Additionally when indicated
- Genital specimen collection
 - At months 6, 12, 18, 24 and study exit
 - If indicated, at the time of suspected or confirmed HIV seroconversion
- Blood draw
 - At months 6, 12, 18, 24 and study exit
 - Additionally when clinically indicated

7.3.3 Pharmacy procedures

- Supply of tenofovir gel
 - Each study visit (except at study exit)
 - Additionally when indicated
- Collection of unused and used applicators from participant
 - Each study visit

- Updating product accountability log
 - Each study visit
 - Additionally when indicated

7.3.4 Laboratory procedures

- Urine pregnancy test:
 - Each study visit
 - Additionally when clinically indicated
- HIV rapid tests
 - Each study visit
 - Additionally when clinically indicated
- HIV confirmatory RNA Polymerase Chain Reaction (PCR)
 - If indicated
- HIV confirmatory Western Blot and/or ELISA
 - If indicated
- Serum, plasma archive
 - Months 6, 12, 18, 24 and at study exit
- HBV assays
 - At study exit
- HSV-2 assays
 - At months 6, 12, 18, 24 and study exit
- Creatinine levels
 - At months 6, 12, 18, 24 and study exit
- Safety bloods (see appendix III for tests)
 - At months 6, 12, 18, 24 and study exit
 - Additionally when clinically indicated
- Genital specimen archive
 - Months 6, 12, 18, 24 and study exit

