2.2 Secondary objectives

To compare women receiving tenofovir gel through family planning services with women receiving tenofovir gel through clinical trial clinics for the following:

1. Safety of tenofovir gel measured by clinical and laboratory adverse event rates, including pregnancy rates and outcomes
2. HIV incidence rates
3. The estimated proportion of reported sex acts covered by two gel doses, self-reported adherence to the tenofovir gel dosing strategy and factors influencing gel use in relation to sexual activity, condom use, and intravaginal practices
4. Self-reported service acceptability and completion rates of quarterly (or 2 monthly in Nur-isterate users) HIV and pregnancy testing
5. HIV viral load among HIV seroconverters
6. Tenofovir resistance of HIV strains from HIV seroconverters
7. Vaginal cytokines to assess the role of genital inflammation in HIV acquisition
8. HSV-2 and HPV incidence rates
9. Tenofovir levels
10. Self-reported product acceptability

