Provision of tenofovir gel and study monitoring for women enrolled in the intervention arm will be done through local family planning services where QI methodology will be used to promote reliable delivery of tenofovir gel and family planning services. Participants in the intervention arm will have monthly visits for the first three months post-enrollment; thereafter, gel provision and monitoring will be scheduled to coincide with each participant's routine family planning visit (typically every 2-3 months). Study visits in the intervention arm will be scheduled no longer than 3 months apart.

Women assigned to the control arm will have monthly scheduled visits at the CAPRISA urban or rural clinic where they will be provided with 1% tenofovir gel.

HIV and pregnancy testing will be performed at each study visit in both study arms. HIV/sexually transmitted infection (STI) risk reduction messages and condoms will be provided to all participants using consistent prevention messages. Similarly, family planning services, tenofovir gel and counseling on product adherence will be provided to all participants. Participants in both study arms will be requested to return all used and unused applicators at each study visit.

Clinical safety will be assessed pre-, during- and post-enrollment. Laboratory safety assessments will be done at enrollment, months 6, 12, 18, 24, study exit and additionally if indicated. At these visits, blood samples will be collected for urea, electrolytes, creatinine, liver function tests, full blood count, calcium and phosphate levels. Pelvic examinations, including naked eye examination of the external genitalia and speculum examination of the vagina and cervix will be conducted at enrollment, months 6, 12, 18, 24, study exit and additionally if indicated. These visits will also include collection of blood for storage of serum and plasma and genital specimens for storage to assess for markers of safety, risk exposure, product adherence, potential post-trial assessments of activity against STIs, and tenofovir resistance. For symptoms experienced between scheduled visits, the participant will be counseled to report to their assigned study site as soon as possible.

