9.2.2 Secondary endpoints

The following secondary endpoints will be assessed:

- Clinical and laboratory adverse event and pregnancy rates
- HIV incidence rates.
- Self-reported adherence to the tenofovir gel dosing strategy (and factors influencing gel use in relation to sexual activity, condom use, and intravaginal practices)
- Self-reported service acceptability and completion rates of quarterly HIV and pregnancy testing
- HIV viral load among HIV seroconverters.
- Tenofovir resistance among HIV seroconverters.
- Vaginal cytokines.
- HSV-2 and HPV incidence rates
- Tenofovir levels (and their correlation with HIV and HSV-2 infection rates)
- Self-reported product acceptability.

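### Pregnancy rates and outcomes are compared between arms, but after month 3 scheduled tests are 28 days apart in control and 2-3 months apart in the family planning arm, so short pregnancies are detected unequally

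*Protocol*

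**What the plan says.** Section 2.2 opens the secondary objectives with a between-arm comparison: "To compare women receiving tenofovir gel through family planning services with women receiving tenofovir gel through clinical trial clinics for the following". The first item is "Safety of tenofovir gel measured by clinical and laboratory adverse event rates, including pregnancy rates and outcomes". Section 9.2.2 lists the matching endpoint as "Clinical and laboratory adverse event and pregnancy rates".

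Testing follows visits. Section 3.1 states: "HIV and pregnancy testing will be performed at each study visit in both study arms". Section 7.3.4 lists the "Urine pregnancy test" for each study visit, with further tests when clinically indicated.

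The visit schedules differ by arm. Section 7.3 states: "Follow-up visits for women enrolled into the control arm are scheduled throughout the study follow-up period on a 28-day schedule". In the family planning arm, sections 3.1 and 7.3 give monthly visits for three months and then visits timed with routine family planning attendance, typically every 2-3 months. Section 3.1 caps the interval at 3 months. The table in section 5 gives 3-monthly visits, or 2-monthly for Nur-isterate users.

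Other routes of detection exist in both arms: a menstrual history covering the interval since the last visit (section 7.3.2) and interim visits (section 7.4).

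**The concern.** A pregnancy that becomes test-positive and ends between two scheduled tests cannot be found by those tests. After month 3 the interval between tests is two to three times longer in one arm, by assignment. The pregnancies missed are those that end early. Under-detection therefore lowers the observed pregnancy rate and removes losses from the outcome mix, which raises the apparent share of live births.

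Both distortions favour the delivery model under study. If true rates were equal, the comparison could still suggest fewer pregnancies or better pregnancy outcomes with family planning delivery, when part of the difference came from less frequent testing. The protocol fixes both the comparison and the unequal schedule, and does not connect the two.

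**Working it through.** The protocol gives no pregnancy rate, expected count or power for this comparison, so there is no figure to reproduce.

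**Scheduled tests per woman.** Section 3.1 gives about 12 months of accrual and about 18 months of follow-up after accrual ends, so 18 to 30 months per woman. A month is taken as 30.44 days.
- Control: 18 × 30.44/28 ≈ 20 tests; 30 × 30.44/28 ≈ 33 tests.
- Family planning, 3-monthly: 3 + 15/3 = 8; 3 + 27/3 = 12.
- Family planning, 2-monthly: 3 + 15/2 = 10.5; 3 + 27/2 = 16.5.
- Share of follow-up on unequal schedules: 15/18 = 83% to 27/30 = 90%.

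**Chance of falling between tests.** Let a pregnancy be test-positive for D days, with tests T days apart and a start that is uniform over the interval. The chance that scheduled tests miss it is max(0, 1 − D/T). T is 28 days in control, and 61 or 91 days in the family planning arm. D is an assumption.

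| D (days) | T = 28 | T = 61 | T = 91 |
|---|---|---|---|
| 14 | 50% | 77% | 85% |
| 28 | 0% | 54% | 69% |
| 42 | 0% | 31% | 54% |
| 56 | 0% | 8% | 38% |
| 70 | 0% | 0% | 23% |

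Averaging over an assumed uniform spread of D gives the mean miss probability m_T:

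| D range (days) | m_28 | m_61 | m_91 |
|---|---|---|---|
| 7-42 | 0.225 | 0.598 | 0.731 |
| 7-70 | 0.125 | 0.380 | 0.577 |
| 14-84 | 0.050 | 0.259 | 0.462 |

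With equal numbers of short pregnancies per arm, the family planning arm holds m_T/(m_T + m_28) of those missed after month 3. This runs from 0.598/0.823 = 73% to 0.462/0.512 = 90%.

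**Effect on the rate ratio after month 3.** Let L be the share of pregnancies ending in such losses, and r the share of missed losses recovered by history, indicated tests or interim visits, taken as equal in both arms. With equal true rates:

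ratio = [1 − L·m_T·(1 − r)] / [1 − L·m_28·(1 − r)]

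L was varied from 10% to 48.1%. The upper value is 1 − 51.9%, from the lower live-birth proportion in CAPRISA 004 (section 1.3).
- r = 0, lowest: (1 − 0.481 × 0.731)/(1 − 0.481 × 0.225) = 0.648/0.892 = 0.73.
- r = 0, highest: (1 − 0.10 × 0.259)/(1 − 0.10 × 0.050) = 0.974/0.995 = 0.98.
- r = 0.8, same two corners: 0.930/0.978 = 0.95, and 0.995/0.999 = 1.00.

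**Effect on outcomes.** The live-birth share among detected pregnancies is (1 − L)/[1 − L·m_T·(1 − r)]. For D of 7-70 days and L = 33.3% (1 − 66.7%, the other CAPRISA 004 arm):
- r = 0: 70% in control against 76% (2-monthly) to 83% (3-monthly).
- r = 0.8: 67% against 68% to 69%.

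**Visit window.** Section 7.3 allows 14 days either side of a visit. If timing is uniform in that window, the control gap is 28 + X days, with X triangular on −28 to 28. At D = 28, control detection is 1 − E[max(0, −X)]/28 = 1 − 4.67/28 = 83%. Family planning gaps still exceed 28 days, so their 54% and 69% misses are unchanged. The window narrows the contrast but does not remove it.

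**The case against.** The strongest reply is that the analysis of secondary objectives is left to the SAP (section 9.5), and that the protocol nowhere says a pregnancy counts only if a scheduled test is positive. The visit frequency is also part of the delivery model being tested (section 5), so it is not an error in itself. This stands in part. The SAP may already deal with the matter, and the schedule needs no change. But the protocol itself sets the comparison and the unequal testing, and a plain comparison of rates would inherit the bias.

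The second reply concerns other routes of detection. A reader might infer that every pregnancy ending between visits goes unrecorded in the family planning arm. The documents do not support that: sections 7.3.2, 7.3.4 and 7.4 provide history, indicated tests and interim visits in both arms, and a recognised loss can be recorded without a positive scheduled test. These routes depend on the woman recognising or reporting the event, and nothing shows that they close the gap.

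Two other strong readings also fail. Control does not detect all short pregnancies: it misses half of those detectable for 14 days, and more once the visit window is allowed for. Nor do the 33-48% of CAPRISA 004 pregnancies without a live birth measure short pregnancies missed between tests. That figure covers all pregnancies without a live birth in that trial, and serves here only to bound L.

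**Conclusion.** The concern holds as unequal ascertainment in a secondary safety comparison. After month 3, scheduled testing finds short pregnancies less often in the family planning arm. With equal true rates, this lowers that arm's observed pregnancy rate and raises its apparent live-birth share. Months 0-3 are essentially comparable, and pregnancies that continue are found later but not lost.

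The size is uncertain. The ranges of 0.73-0.98 (no recovery) and 0.95-1.00 (80% recovery) rest on assumed values of D, L and r, on equal recovery in both arms, and on tests at their nominal dates. They describe the period after month 3, and including months 0-3 would dilute them. If recovery is high, the bias may be small. Because no expected pregnancy count is given, the documents do not show whether it would change a conclusion. Nothing here bears on the primary endpoint of returned used applicators.

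**What to change.** Keep every detected pregnancy and its outcome in the safety report by arm, with the route of detection: scheduled test, indicated test or history. State there that the all-tests difference between arms is subject to unequal detection.

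Base between-arm inference on ascertainment common to both arms:
- Compare months 0-3 directly.
- After month 3, count pregnancies that are positive at visits on a grid common to both arms, with their outcomes. A control pregnancy seen only off the grid stays in the safety report but not in this comparison.
- Set the grid independently of contraceptive choice after randomization, which delivery through family planning could influence. Scheduled 3-monthly time points are one option, although women on 2-monthly visits will not attend at all of them. The visits at months 6, 12, 18, 24 and exit, which section 7.3 sets for all participants, are another, but retain fewer pregnancies.

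Replacing the full count with the grid count would drop documented safety events, so the two should stand side by side. The cost is analysis wording and a derived variable from data already collected. No participant's testing changes. The downside is fewer counted pregnancies, and so less precision, in the common-grid comparison.
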